12.1	STATISTICAL DESIGN.....	21
12.2	INTERIM ANALYSES.....	21
12.3	DESCRIPTIVE STATISTICS AND EXPLORATORY DATA ANALYSIS	21
12.4	PRIMARY ANALYSIS	21
12.5	SECONDARY ANALYSIS	22
13.	REFERENCES	24
APPENDICES.....		25
	APPENDIX A: PARTICIPANT ELIGIBILITY CHECKLIST	ERROR! BOOKMARK NOT DEFINED.

PROTOCOL SYNOPSIS

In the table below summarize the basic aspects of this research. This is to be used as a quick reference guide. Remove any section that is not relevant to the research.

TITLE	A Randomized Double-blinded, Placebo-Controlled Trial: Use of Transversus Abdominis Plane (TAP) Block in Breast Cancer Patients Undergoing Microsurgical Breast Reconstruction with Abdominal Free Flap
STUDY PHASE	Phase III
INVESTIGATIONAL PRODUCT OR PROCEDURE	Pre-operative Transversus Abdominis Plane Block with Nimbus Ambulatory Infusion System
PRIMARY OBJECTIVE(S)	Post-operative narcotic usage
SECONDARY OBJECTIVE(S)	
 i. Post-operative pain scores ii. Post-operative anti-emetic usage iii. Time to ambulation iv. Time to first bowel movement v. Patient-perceived quality of life
TREATMENT SUMMARY	
Two study arms:
 
 • Intervention: infusion of 0.125% bupivacaine through TAP catheter • Control: infusion of saline through TAP catheter
SAMPLE SIZE	128

SCHEMA

LIST OF ABBREVIATIONS AND DEFINITION OF TERMS

Include additional abbreviations as needed. Remove any unnecessary abbreviations.

AE	Adverse event
CRF	Case report form
IRB	Institutional Review Board
IV	Intravenous
MG	Milligrams
ML	Milliliter
OME	Oral morphine equivalent
PCA	Patient-controlled analgesia
PD	Protocol director
PO	Per os
POD	Post-op day
Q4H	Every 4 hours
RCT	Randomized controlled trial
SAE	Serious adverse event
TAP	Transversus abdominis plane
VAS	Visual analog scale
VTBI	Volume to be infused

1. OBJECTIVES

1.1. Primary Objective

The primary objective is to determine if pre-operative transversus abdominis plane (TAP) blocks with continued infusion of local anesthetic post-operatively affect post-operative narcotic usage as compared to a placebo TAP block.

1.2. Secondary Objectives

1.2.1 To determine if pre-operative TAP blocks with continued infusion of local anesthetic post-operatively affect post-operative pain scores as compared to a placebo TAP block.

1.2.2 To determine if pre-operative TAP blocks with continued infusion of local anesthetic post-operatively affect anti-emetic usage as compared to a placebo TAP block.

1.2.3 To determine if pre-operative TAP blocks with continued infusion of local anesthetic post-operatively affect time to ambulation post-operatively as compared to a placebo TAP block.

1.2.4 To determine if pre-operative TAP blocks with continued infusion of local anesthetic post-operatively affect time to first bowel movement as compared to a placebo TAP block.

1.2.5 To determine if pre-operative TAP blocks with continued infusion of local anesthetic post-operatively affect patient-reported quality of life as compared to a placebo TAP block.

2. BACKGROUND

2.1 Study Disease

Patient enrolled in our study with have a known or presumed diagnosis of breast cancer or are pursuing prophylactic treatment for which they are undergoing post-mastectomy breast reconstruction with abdominal free flap.

2.2 Study Agent/Device/Procedure

2.2.1 Nimbus Ambulatory Infusion System:

Product Description:

- Adjustable volume to be infused (VTBI), variable basal rate and bolus delivery
- Single patient use.

The Nimbus Ambulatory Infusion System is capable of carrying:

- Time stamped infusion parameters
- Incidences of bolus requests vs. bolus delivered

2.2.2 Transversus abdominis plane (TAP) block

The transversus abdominis plane (TAP) block is a peripheral nerve block that targets nerve roots T6 to L1, which innervate the anterior abdominal wall. The block is placed by administering local anesthetic into the fascial plane between the internal oblique muscle and the transversus abdominis muscle.^{1, 2} TAP blocks have previously been shown to improve immediate post-operative patient comfort and reduce post-operative narcotic usage in a variety of other abdominal surgeries including abdominoplasty, laparotomy, and cesarean section.³⁻⁷

2.2.3 Bupivacaine (Bupivacaine Hydrochloride)

Bupivacaine hydrochloride is an amide-type local anesthetic metabolized primarily in the liver via conjugation with glucuronic acid. Peak levels of bupivacaine in the blood are reached in 30 to 45 minutes following peripheral nerve block injection, followed by a decline to insignificant levels during the next three to six hours. The half-life of Bupivacaine Hydrochloride in adults is 2.7 hours. When administered in recommended doses and concentrations, Bupivacaine Hydrochloride does not ordinarily produce irritation or tissue damage.⁸

For clinicaltrials.gov compliance

Both the Nimbus Ambulatory Infusion System and the local anesthetic bupivacaine have been FDA approved for use for analgesia in patient in the United States.

2.3 Rationale

There are many options for post-mastectomy breast reconstruction including implants, pedicled muscle flaps, and free muscle flaps. With the development of advanced microsurgical techniques, free abdominal muscle flaps have become a popular option for breast reconstruction.^{9, 10} For these patients, the speed of recovery and hospital length of stay following surgery are largely determined by the abdominal flap donor site rather than the breast recipient and resection site.

Successful post-operative analgesia has been reported to decrease the incidence of both cardiopulmonary complications, in-hospital mortality, and healthcare costs, and it may also contribute to lower odds of death after surgery.^{11, 12} In addition, when examining factors leading to expedited discharge following abdominal-based breast reconstruction surgery, use of a multimodal pain regimen was found to be predictive of successful early discharge.¹³ Though post-operative opioids can decrease pain scores, opioids can also lead to adverse side effects including sedation, nausea, vomiting, constipation, and respiratory depression.¹⁴ Because patients undergoing abdominal flap-based breast reconstruction have had abdominal muscle tissue manipulation, postoperative vomiting can increase the risk of incisional hernias and other surgical complications.

An increasingly utilized option for post-surgical pain management is a pre-operative nerve block targeting anesthetic directly to the nerve roots innervating the surgical field. In the setting of abdominal flap-based breast reconstruction, a transversus abdominis plane (TAP) nerve block accomplishes this goal for the abdominal incision. Several studies have evaluated the TAP block in abdominal flap-based breast reconstruction. Hivelin et al. evaluated bilateral ultrasound-guided TAP block in patients undergoing unilateral deep inferior epigastric perforator (DIEP) flap reconstruction and found that patients reported lower pain scores post-operatively and demonstrated lower narcotic usage in the first 24 hours, but not in subsequent time periods out to

48 hours after surgery. However, in this study only a single injection of local anesthetic was given intra-operatively, and this injection was performed by a surgeon in the operating room, rather than by an anesthesiologist in the pre-operative waiting area. The duration of block placement varied between 18 and 24 minutes, increasing the overall length of time in the operating room. In addition, Hivelin et al. only followed patients to 48 hours after reconstruction.¹⁵ Furthermore, Wheble et al. performed a retrospective review of intra-operatively placed TAP blocks and found patients receiving the block had a shorter hospital length of stay, lower overall morphine usage, and less post-operative nausea and vomiting. However, this was a retrospective study with a small number of patients in each group (12 in the TAP group, and 15 in the non-TAP group).¹⁶

In addition, Zhong et al. conducted a prospective cohort study with TAP block catheters placed intra-operatively under direct visualization of fascial planes, and the anesthetic infusions continued until post-operative day 3. Zhong et al. compared this group of patients to a retrospective cohort from the same institution and found that patient who received TAP blocks had significantly less opioid usage than those who did not.¹⁷ The group conducted a subsequent randomized double-blinded controlled trial with TAP catheters placed under direct vision, this time administering either local anesthetic or saline for controls and found similar results.¹⁸

A limitation of both studies by Zhong et al. is that patients undergoing both unilateral and bilateral reconstruction were combined, as were patients undergoing immediate and delayed reconstruction. Given that patients are subjected to twice the surgical insult in bilateral versus unilateral reconstruction, combining these patients into one cohort for analysis of post-operative pain may confound the results attained. Similarly, in delayed reconstruction, a repeat surgical incision is made at the site of the breast, whereas in immediate reconstruction, the same incision at the breast is used for both mastectomy and reconstruction.

In our study design, patients undergoing unilateral and bilateral reconstruction will be separated for both randomization and statistical analysis. We aim to further elucidate if the specific type of surgery changes the efficacy of the pre-operative TAP nerve block.

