3.1 Inclusion Criteria

- 3.1.1 Prior diagnosis or presumed diagnosis of breast cancer or undergoing prophylactic treatment.
- 3.1.2 Greater than 18 years old.
- 3.1.3 Female.
- 3.1.4 Undergoing microsurgical breast reconstruction with abdominal free flap.
- 3.1.5 Ability to understand and the willingness to sign a written informed consent document.

3.2 Exclusion Criteria.

- 3.2.1 True allergy to local anesthetics or opioids.
- 3.2.2 History of addiction to narcotics within the last 24 months
- 3.2.3 History of chronic pain on opioids within the last 24 months.
- 3.2.4 Specific mental health issues such as schizophrenia or bipolar disorder.
- 3.2.5 Patients who are pregnant.

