3.4 Randomization Procedures

Patients will be randomized within their surgery subtype (unilateral or bilateral) by the Stanford

Pharmacy to receive TAP catheters infusing either bupivacaine or saline. Randomization will occur using a computer software program to be implemented by the Pharmacy. The anesthetist placing the block, the surgeon performing the surgery, the nurses caring for the patient while hospitalized, and the research coordinators collecting data will be blinded to the randomization status.

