12.1.1 Randomization

Patients will be randomized within their group (unilateral or bilateral reconstruction) to receive either a true TAP catheter or a sham TAP catheter with saline infusion. The Stanford Pharmacy will randomize patients into the two groups.

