12.4.2. Analysis Plan

Differences between the two arms will be evaluated using an analysis of covariance model. The comparison of the two arms will be made adjusting for the variables used in the stratified randomization. The primary analysis will be a modified intent-to-treat principle (using recorded values where available regardless of compliance).

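### Immediate versus delayed timing is raised in the Rationale as a limitation of earlier studies but is absent from the ANCOVA; pre-specifying it as a covariate would be a cheap, modest gain in precision.

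*Combined protocol and SAP*

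**What the plan says.** Section 2.3 lists two features of the earlier studies as limitations. One is that unilateral and bilateral cases were analysed together. The other is introduced with the words "as were patients undergoing immediate and delayed reconstruction". The protocol says that mixing by laterality may confound the findings. It then turns to timing and gives a physical reason why it could matter: "in delayed reconstruction, a repeat surgical incision is made at the site of the breast", whereas an immediate reconstruction uses the mastectomy incision.

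The same section then states what this trial does differently: "patients undergoing unilateral and bilateral reconstruction will be separated for both randomization and statistical analysis". Timing is not part of that statement, and it does not come up again:

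- Eligibility (3.1.4) reads "Undergoing microsurgical breast reconstruction with abdominal free flap" and has no restriction on timing. The checklist in Appendix A has none either.
- Section 3.4 begins "Patients will be randomized within their surgery subtype (unilateral or bilateral", and 12.1.1 repeats the rule: "Patients will be randomized within their group (unilateral or bilateral reconstruction". Laterality is the only stratification factor.
- Section 12.4.2 sets the primary model, "Differences between the two arms will be evaluated using an analysis of covariance model", and its covariates: "The comparison of the two arms will be made adjusting for the variables used in the stratified randomization".
- In 12.5, the models for anti-emetic use, ambulation and bowel movement adjust for the same variables. Pain and quality of life are compared by t-test without covariates.
- The study calendar (section 9) has no item for timing, and 12.3 still holds template text.

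**The concern.** The protocol treats timing as a feature that could affect post-operative pain and then makes no use of it. No section says outright that both timings will be pooled. That follows from the absence of any restriction, stratification or adjustment.

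If timing does influence opioid use, its contribution stays in the residual variance of the ANCOVA, and the confidence interval for the difference between arms is wider than it need be. The trial is sized for only 80% power, with no stated allowance for dropout, so a nearly free gain in precision is worth having. Naming the covariate in advance also avoids a later argument over whether to add it if the arms happen to differ in timing.

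**Working it through.** **Inputs from the documents (12.6.1 and 12.6.2).** SD of total oral morphine equivalents 20 mg; target difference 10 mg; two-tailed t-test; 80% power; 64 per arm, 128 in total.

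**Assumed, because the documents do not say.** Two-sided alpha 0.05; share delayed p between 0.2 and 0.5; timing effect g of 5, 10 or 15 mg; timing binary and independent of laterality.

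**Step 1: reproduce the plan's figure.** With the noncentral t distribution, power is 79.5% at 63 per arm and 80.1% at 64. The stated 64 per arm is therefore reproduced, which also supports alpha 0.05.

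**Step 2: effect of adjusting for timing.** A binary factor with prevalence p and effect g explains the fraction R² = p(1 − p)g²/20² of the variance, so the residual SD is 20 × √(1 − R²). For p = 0.5 and g = 10: R² = 0.25 × 100/400 = 0.0625, and the residual SD is 20 × √0.9375 = 19.36 mg. Power is recomputed at 64 per arm with one further degree of freedom charged.

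| Timing effect | Residual SD, 20% delayed | Power, 20% delayed | Residual SD, 50% delayed | Power, 50% delayed |
|---|---|---|---|---|
| none | 20.00 mg | 80.1% | 20.00 mg | 80.1% |
| 5 mg | 19.90 mg | 80.5% | 19.84 mg | 80.8% |
| 10 mg | 19.60 mg | 81.7% | 19.36 mg | 82.6% |
| 15 mg | 19.08 mg | 83.7% | 18.54 mg | 85.7% |

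The row for no effect is the base case without timing in the model. Confidence-interval width scales with the residual SD. At 50% delayed it narrows by about 0.8% for a 5 mg effect (19.84/20 = 0.992) and about 3% for a 10 mg effect (19.36/20 = 0.968).

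**Step 3: is chance imbalance a further error?** Take p = 0.5 and g = 10.

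- Variance of the difference without timing: 400 × 2/64 = 12.50 mg².
- Variance with timing in the model: 375 × 2/64 = 11.72 mg².
- Reduction: 0.78 mg².
- SD of the between-arm difference in share delayed: √(2 × 0.25/64) = 0.0884.
- Variance of the resulting shift in the estimate: (10 × 0.0884)² = 0.78 mg².

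The two figures are the same quantity. The unadjusted standard error already contains the effect of chance imbalance in timing.

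**Limit of the calculation.** It covers the linear model for the primary outcome only. No gain has been computed for the secondary models.

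**The case against.** The strongest reply is that adjusting only for the stratification variable is a legitimate pre-specified choice, and that the plan meets its 80% power without timing. That stands, and it is why the point is low in severity.

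The assumed effects can also be challenged. An effect of 10 or 15 mg would make timing matter as much as, or more than, the difference that 12.6.2 calls clinically relevant, and no section supports that. Section 2.3 says that recovery and length of stay depend mainly on the abdominal donor site, while the timing difference it describes is at the breast. This suggests a small effect but does not settle it: the statement concerns recovery rather than opioid use, and the primary outcome (10.1.1) sums all narcotics, whichever site hurts. A 50/50 split is also the most favourable case for a binary covariate, so the range down to 20% delayed is shown. Mixed timing can occur only in bilateral patients, so part of what timing explains may already be removed by laterality.

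A reader might infer more than the documents support:

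- *That the trial claims to have solved the timing problem and has not.* Section 2.3 promises separation by laterality only. Timing is a remark left without follow-up, and no stated design feature is contradicted.
- *That timing is an established prognostic factor.* The protocol describes a difference in incision and reports no effect on pain or opioid use. Its remark about confounding is attached to laterality.
- *That the result will be confounded as in the earlier studies.* One of those was a cohort compared with a retrospective group, where case mix can bias the comparison systematically. In this randomised trial the estimate stays unbiased and the test valid without timing in the model.
- *That chance imbalance is a second harm beside lost precision.* Step 3 of the working shows that it is the same variance.

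**Conclusion.** The point holds as a cheap improvement of low severity. The plan raises timing, admits both kinds of patient, and neither stratifies by timing nor adjusts for it. The consequence is limited to precision. Under the stated assumptions the gain in power ranges from under 1 percentage point (5 mg timing effect) through about 2 points (10 mg) to roughly 4 to 6 points (15 mg). The true size is unknown because the documents give neither the timing mix nor its effect, and overlap with laterality would reduce it.

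**What to change.** Record planned timing before randomisation, from the surgical plan, as immediate, delayed, or mixed for bilateral cases. In 12.4.2, name it as a pre-specified covariate beside laterality, and do the same in the adjusted models of 12.5 (anti-emetic use, ambulation, first bowel movement). Randomisation and sample size do not change.

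The cost is one CRF field and one or two degrees of freedom out of 125 (128 patients less one each for the intercept, arm and laterality). The downside is that the gain is negligible if timing shifts opioid use by 5 mg or less.

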12.4.1 Analysis Population

Subjects will be grouped according to laterality of breast reconstruction (i.e., unilateral vs. bilateral). Within each group, experiment subjects will be compared to control subjects. A first

sensitivity analysis will explore the impact of missing data by replacing missing data with the more extreme values that favor the null hypothesis. A second sensitivity analysis will replace missing values with an extreme value that favors the alternative hypothesis. In both cases "extreme" is the largest or smallest value as applicable.

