12.6.2 Sample size justification

The target sample size was determined by the two-tailed t-test power calculation. The estimated standard deviation of total oral morphine or equivalents is 20 mg. A difference of 10 mg between the two arms is considered clinically relevant. To detect a difference of 10mg of morphine (or oral morphine equivalents) between the experimental and control groups with a power of 80%, we calculated a target enrollment of 64 patients in each group. The null hypothesis is that the experiment and control groups will not have significantly different Post-operative Narcotic Usages in the first 48-hour period post-operatively. The alternative hypothesis is that the experiment and control groups will have significantly different Post-operative Narcotic Usages in the first 48-hour period post-operatively

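### The Rationale asks whether surgery type changes the block's efficacy, but Section 12 plans no test or estimate of the difference between the unilateral and bilateral effects

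*Combined protocol and SAP*

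**What the plan says.** Section 2.3 criticises earlier trials for combining unilateral and bilateral patients, and states that "patients undergoing unilateral and bilateral reconstruction will be separated for both randomization and statistical analysis". It then gives the aim: "We aim to further elucidate if the specific type of surgery changes the efficacy of the pre-operative TAP nerve block". Section 3.4 makes laterality the stratification factor: "Patients will be randomized within their surgery subtype (unilateral or bilateral").

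For the primary outcome, Section 12.4.1 groups patients by laterality and adds: "Within each group, experiment subjects will be compared to control subjects". Section 12.4.2 says: "Differences between the two arms will be evaluated using an analysis of covariance model", and then: "The comparison of the two arms will be made adjusting for the variables used in the stratified randomization".

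The secondary analyses follow one of these patterns:
- Pain scores (12.5.1) are compared by t-test within laterality groups.
- Anti-emetic use, time to ambulation and time to first bowel movement (12.5.2 to 12.5.4) are compared between arms with adjustment for the stratification variable.
- Quality of life (12.5.5) is compared between arms by t-test.

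None of these sections mentions an interaction term, a heterogeneity test, or an estimate of how far the two laterality-specific effects differ. No rule is given for interpreting strata that disagree. The aim in Section 2.3 does not reappear in the synopsis objectives, in Sections 1.1 and 1.2, in the outcome measures of Section 10, or in the hypotheses of Section 12.6.2.

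**The concern.** Whether surgery type changes efficacy is a question about the difference between two treatment effects. Comparing arms within each laterality group yields two effects but no planned contrast between them. Adjusting an ANCOVA for laterality, on its natural reading, enters laterality as a main effect and estimates a single common treatment effect, which leaves the question out of the model.

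If the report then shows a significant result in one group and not in the other, a reader may take this as evidence that laterality matters. That inference is unsound. Each group holds only part of a sample that was sized for one overall comparison, so disagreement in significance is common even when the true effects are identical. Agreement in significance can equally conceal a real difference in size.

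Deciding whether 12.4.1 or 12.4.2 defines the primary comparison would not settle this. Either choice leaves the contrast between the two effects unplanned.

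**Working it through.** **Inputs from Section 12.6:** SD 20 mg oral morphine equivalents; relevant difference 10 mg; power 80%; 64 patients per arm, 128 in total. On the test: "The target sample size was determined by the two-tailed t-test power calculation".

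**Assumptions, not in the documents:** alpha 0.05; laterality splits of 50:50, about 70:30 and about 80:20; the same SD in both groups; 1:1 allocation within groups; no missing data.

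**Step 1: reproduce the plan's figure.** With a two-sided alpha of 0.05 and the noncentral t distribution, 63 per arm gives 79.5% power and 64 per arm gives 80.1%. The plan's 64 is reproduced, which supports the assumed alpha. The normal-approximation formula with a one-sided 0.05 gives 50 per arm, which does not match.

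**Step 2: power within each laterality group.** With n per arm in a group, the noncentrality is 10 / (20 × √(2/n)) on 2n − 2 degrees of freedom. The true effect is set to 10 mg in both groups.

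**Step 3: chance that exactly one group is significant.** With p1 and p2 the two powers, this is p1(1 − p2) + p2(1 − p1).

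| Split (n per arm in each group) | p1 | p2 | Exactly one significant |
|---|---|---|---|
| 50:50 (32 and 32) | 50.4% | 50.4% | 50% |
| about 70:30 (45 and 19) | 65.0% | 32.3% | 55% |
| about 80:20 (51 and 13) | 70.6% | 23.2% | 61% |

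With no effect in either group, the chance is 2 × 0.05 × 0.95 = 9.5%. A direct interaction test would be falsely positive in 5% of trials, whether the common effect is 10 mg or zero.

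**Step 4: precision of the direct contrast.** The SE of the difference between the two effects is 20 × √(2/n1 + 2/n2). At 50:50 this is 20 × √(2/32 + 2/32) = 7.07 mg. The 95% CI half-width is about 1.98 × SE (124 degrees of freedom), and the difference detectable with 80% power is about 2.80 × SE.

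| Split | SE | 95% CI half-width | Power for a 10 mg difference in effects | Difference with 80% power |
|---|---|---|---|---|
| 50:50 | 7.07 mg | 14.0 mg | 29% | 19.8 mg |
| about 70:30 | 7.74 mg | 15.3 mg | 25% | 21.7 mg |
| about 80:20 | 8.79 mg | 17.4 mg | 20% | 24.6 mg |

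For scale, 80% power for a 10 mg difference in effects at a 50:50 split would need 16 × 20² × (1.960 + 0.842)² / 10², or about 503 patients.

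**The case against.** **The aim is only in the Rationale.** This stands. No listed objective, outcome measure or hypothesis concerns effect modification, so the contrast belongs in the plan as exploratory. The aim is still stated, and the same paragraph presents it alongside separating the groups for randomization and analysis.

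**Nothing shows that the investigators will misread discordant strata.** This also stands. A reader might infer that the plan adopts significance in one group but not the other as its criterion. The documents contain no such rule. What can be said is that they contain no rule at all, so the misreading is possible and nothing in the text guards against it.

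**The within-group comparisons already supply what is needed.** Partly right. Two independent estimates with standard errors allow the difference and its CI to be computed, so it would be wrong to say that the aim can be addressed only by comparing two p-values. The gap is that the contrast is not prespecified. If added after results are known, it is post hoc.

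**Main-effects ANCOVA is an interpretation.** True. Section 12.4.2 speaks only of adjustment. A main effect is the natural reading, and no interaction term is named under any reading.

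**The interaction test is weak.** True, as the working shows. This is a reason to report an interval and state the limit. The side-by-side comparison uses the same patients and is no more informative.

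**Type of surgery may be wider than laterality.** Section 2.3 also discusses immediate versus delayed reconstruction. Only laterality is carried into randomization and analysis, so the point is confined to it.

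**Conclusion.** The point holds as an omission: the plan states an effect-modification aim in its Rationale and specifies no analysis that tests or estimates it. No listed objective or hypothesis is affected, and the overall sample size calculation reproduces.

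The risk of misreading is substantial if the block works equally well in both groups: discordant significance in about 50–61% of trials over the splits shown. It falls to 9.5% if there is no effect in either group. These figures rest on the plan's SD and 10 mg difference, an assumed two-sided alpha of 0.05, and laterality splits that the documents do not give.

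The 80%-power difference of about 20–25 mg should not be taken as a detection limit. At a 50:50 split, an observed difference in effects of about 14 mg would already reach significance.

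**What to change.** In Section 12.4.2, add an exploratory secondary ANCOVA of 48-hour oral morphine equivalents with arm, laterality and arm-by-laterality as terms.

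- Report the difference between the two laterality-specific effects with its 95% CI, next to each laterality-specific estimate and its CI.
- State that any claim that laterality changes efficacy rests on that contrast, and not on significance in one group and its absence in the other.
- State the expected precision, with its assumptions: SE about 7.1–8.8 mg; power about 20–29% for a 10 mg difference in effects; 80% power only for about 20–25 mg, depending on the split.
- State alpha, which Section 12.6.2 leaves out.

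The cost is one model term and a few lines of text. Laterality is already recorded for randomization, so no further patients or data are needed. The downside is one extra exploratory analysis with admittedly low power.
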